9.7.1.6.2. Best Corrected Visual Acuity (BCVA)

Descriptive summaries of the observed values of logMAR at each scheduled visit as well as the change from baseline at each post-baseline visit will be presented for both eyes. A categorical analysis of subjects who lose 0.3 lines ETDRS in either eye at each visit or final visit will be conducted.

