7.1.3 Visit 3 (Day 1)

The following procedures will be performed at Visit 3 (Day 1). Ophthalmic procedures should be performed in the order suggested below:

- BCVA
- Biomicroscopy
- IOP
 - Measured using Goldmann applanation tonometer and a two-person reading method.
 - Reading at:
 - 8:00AM (± 30 mins)
 - Measure twice in each eye; if results differ by >1 mm Hg, a third measurement will be obtained. The mean will be taken if two measurements are used, for 3 measurements record the median.
- Administer first dose of study drug in clinic after IOP is taken.
- Dispense study drug
- Instruct subject to dose daily in the morning (suggested timing between 7:00AM and 9:00AM).
- Blood pressure & heart rate
- Update concomitant medications, as needed
- Adverse event assessment

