12.3.2 Best Corrected Visual Acuity

Visual Acuity will be assessed at each visit in monocularly in both eyes, testing the right eye first and then the left eye.

The subject should be positioned according to the elevation of the chart (either seated or standing) so that the chart is at a comfortable viewing angle. The subject should attempt to read each letter, line-by-line, left to right, beginning with line 1 at the top of the chart. The subject should be told that the chart has letters only, no numbers. If the subject reads a number, they should be reminded that the chart contains no numbers, and the examiner should then request a letter instead of the number. The subject should be asked to read slowly, about 1 letter per second, to achieve the best identification of each letter. The subject is not to proceed to the next letter until they have given a definite response. If the subject changes a response before he has read aloud the next letter, then the change must be accepted.

Maximum effort should be made to identify each letter on the chart; the subject should be encouraged to guess. When it becomes evident that no further meaningful readings can be made, the examiner should stop the test. The number of letters missed or read incorrectly should be noted.

In order to provide standardized and well-controlled assessments of visual acuity during the study, the same lighting conditions must be used consistently throughout the study

Calculations: LogMAR VA = Baseline value + (n x 0.02)

- where: the baseline value is the LogMAR number of the last line read (at least 1 letter read correctly in this line), and “n” is the total number of letters missed up to and including the last line read, and “0.02” is the value for each letter.

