9.5.1.4.2. Best Corrected Visual Acuity (BCVA)

The BCVA will be measured on both eyes in LogMAR at every study visit using Early Treatment Diabetic Retinopathy Study (ETDRS) charts. LogMAR is calculated as Baseline value + (n × 0.02); where the baseline value is the LogMAR number of the last line read (at least one letter read correctly in this line), “n” is the total number of letters missed up to and including the last line read, and “0.02” is the value for each letter.

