9.7.1. Statistical and Analytical Plans

General Conventions

Summary statistics for the data collected during this study will be presented to give a general description of the patients studied. Data from all sites will be combined in the computation of these descriptive summaries. Categorical variables will be summarized by the frequency and percentage of patients in each category. Continuous variables will be summarized using N, mean, standard deviation (SD), median, minimum, and maximum values.

Number of subjects, minimums, and maximums will be calculated to the same number of decimal places as the source data. Means, medians, standard deviations, standard errors, and quartiles will be calculated to one more decimal place than the source data. Percentages will be calculated to the nearest one decimal place and will use the number of non-missing responses as the denominator, unless otherwise noted. Zero count cells will be displayed as "0" with percentage of (0%). Unless otherwise noted, summaries will be performed by the treatment group and presented in the order of: VVN539, 0.04%; VVN539, 0.02%; Vehicle.

Statistical tests will be presented as two-sided p-values rounded to four decimal places; p-values less than 0.0001 will be presented as '<0.0001' and p-values = 1 will be presented as '>0.9999' in all tables. Unless otherwise indicated, statistical testing will be carried out at the $\alpha = 0.05$ significance level.

Baseline values will be defined as the last scheduled or unscheduled measurement prior through Visit 2. Ocular measurements will use the most recent measurement for each eye.

Numeric laboratory data may be recorded at limits of detection (with a '<' or '>' sign, i.e. <0.1 or >0.1). To summarize the data, the original value will be converted to one unit less or more at the level of measured precision (e.g. 0.4 in the case of <0.5 and to 0.6 in the case of >0.5). The actual values will be presented in the data listings.

All data collected in this study will be presented in individual patient data listings for all patients.

Computations for all results will be performed using SAS (Version 9.4, SAS/STAT 15.2) computer software package (SAS Institute, Inc, 2013, 2020), unless otherwise specified.

Strata and Covariates

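### The SAP's only categorical vision-loss threshold is written as 0.3 ETDRS lines (about 1.5 letters); 0.3 on the SAP's own logMAR scale would be 15 letters

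*SAP*

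**What the plan says.** SAP 9.7.1.6.2 first plans descriptive summaries of logMAR, observed and as change from baseline. It then adds: "A categorical analysis of subjects who lose 0.3 lines ETDRS in either eye at each visit or final visit will be conducted". The sentence contains no inequality.

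The scale is set out in SAP 9.5.1.4.2: "The BCVA will be measured on both eyes in LogMAR at every study visit using Early Treatment Diabetic Retinopathy Study (ETDRS) charts". The score is the logMAR value of the last line read plus 0.02 for each letter missed, and the SAP says that 0.02 "is the value for each letter". Protocol 12.3.2 gives the same formula.

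No other vision-loss threshold appears in either document. Protocol 9.4.3.3 plans only summary statistics for BCVA. The one other acuity cut-off, inclusion criterion 4 in Protocol 4.1, concerns eligibility and is in logMAR (+1.0). SAP 9.8.2, which lists changes from the protocol's analyses, does not mention the threshold.

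**The concern.** The sentence attaches a number that makes sense in logMAR to a unit, lines, in which it does not. A third of a line is less than two letters, whereas 0.3 logMAR is 15 letters. The SAP is what the programmer works from, and its text does not settle which of the two would be coded.

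The trial is first-in-human, and its secondary objective is ocular and systemic safety. This is the plan's only count of subjects with vision loss by arm. With the literal cut-off, the table would mostly count ordinary variation between visits in every arm, and a real difference would be hard to see in it.

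**Working it through.** The threshold is a definition rather than a derived figure, so there is no stated result to reproduce. The check is a unit conversion, followed by the share of subjects each reading would flag when nothing has changed.

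**Inputs**
- From the documents: 0.02 logMAR per letter (SAP 9.5.1.4.2, Protocol 12.3.2); threshold number 0.3 (SAP 9.7.1.6.2); 20 subjects per arm (SAP 9.7.2).
- Assumed: 5 letters per ETDRS line, varied from 3 to 6; normally distributed change with mean 0; between-visit SD of the change in one eye of 1 to 5 letters (0.02 to 0.10 logMAR); between-eye correlation of 0 to 0.5.

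**Conversion**
- One line = 5 × 0.02 = 0.1 logMAR.
- Literal reading: 0.3 lines = 0.3 × 5 = 1.5 letters = 1.5 × 0.02 = 0.03 logMAR. Score differences are multiples of 0.02, so exactly 0.03 cannot occur. Read as a minimum, the rule flags a loss of 2 letters (0.04 logMAR) or more.
- logMAR reading: 0.3 / 0.02 = 15 letters, an attainable change. This step needs only the documents' own figure. At 5 letters per line it is 0.3 / 0.1 = 3 lines.
- Ratio: 15 / 1.5 = 10.
- At 3, 4, 5 or 6 letters per line, 0.3 lines is 0.9, 1.2, 1.5 or 1.8 letters. It is never a whole letter. As a minimum it flags a 1-letter loss in the first case and a 2-letter loss in the other three.

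**Subjects flagged at one visit with no true change, literal reading**

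Per eye: p = 1 − Φ(1.5 / SD). Either eye, correlation 0: 1 − (1 − p)². Either eye, correlation 0.5: one minus the bivariate normal probability that both eyes stay at or below 1.5 letters lost.

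| SD of change (letters) | Per eye | Either eye, correlation 0 | Either eye, correlation 0.5 |
|---|---|---|---|
| 1 | 0.067 | 0.129 | 0.115 |
| 2 | 0.227 | 0.402 | 0.349 |
| 3 | 0.309 | 0.522 | 0.454 |
| 5 | 0.382 | 0.618 | 0.541 |

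The either-eye range is 0.115 to 0.618. Per arm that is 20 × 0.115 = 2.3 to 20 × 0.618 = 12.4 subjects.

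**Same calculation at 15 letters**

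The cut is 14.5 letters on the continuous scale. At the largest SD, 5 letters, p = 1 − Φ(14.5 / 5) = 0.00187 per eye. For either eye at correlation 0 it is 1 − (1 − 0.00187)² = 0.0037, or about 0.4%.

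**The case against.** The strongest reply is that context makes the meaning plain. The preceding sentence is in logMAR, the scoring is in logMAR and the eligibility limit is in logMAR, so a sensible programmer would code 0.3 logMAR. That is probably so, but the sentence names a different unit and no other text overrides it.

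A second reply is that little depends on it. SAP 9.7.1.6 plans no treatment comparisons for safety unless specified. The logMAR "change from baseline at each post-baseline visit will be presented for both eyes", and SAP 9.7.1 requires that "Continuous variables will be summarized using N, mean, standard deviation (SD), median, minimum, and maximum values". All data are listed and adverse events are recorded separately. A 15-letter loss would therefore still be seen, and the count could be rebuilt from data already collected. This stands, and it limits the consequence to one descriptive table. The other summaries do not, however, give the number of subjects per arm with a defined loss.

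Third, the flag rates rest on assumptions outside the documents, and their range is wide. That also stands. If the two eyes moved together perfectly, the either-eye rate would fall to the per-eye column, 6.7% to 38.2%; at a correlation of 0.95 it is about 8% to 43%. At the low end, about 2 of 20, the table is contaminated rather than useless. The unit error itself does not depend on these assumptions.

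Finally, a cut-off need not be an attainable score. That is correct: the impossibility of a 1.5-letter change signals a slip, but the harm comes from the cut-off acting at about 2 letters.

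**Conclusion.** The threshold is wrong as written. It mixes two scales, and the two readings differ tenfold at 5 letters per line: 0.03 logMAR (1.5 letters) against 0.3 logMAR (15 letters). The 15-letter figure follows from the documents alone; the 1.5-letter figure and the 3-line equivalent need the assumed 5 letters per line.

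Coded literally, the table would flag about 12% to 62% of unchanged subjects per visit, against at most 0.4% at 0.3 logMAR, under the SD and correlation ranges stated above. The effect is confined to this descriptive safety count. Efficacy results and the sample size are not touched. That 0.3 logMAR was intended is very likely but unconfirmed.

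**What to change.** Ask the sponsor to confirm the intended unit. Then, before unmasking, replace the sentence in SAP 9.7.1.6.2 with one that uses a single scale, an explicit inequality and named visits. For example: subjects with a worsening (increase) from baseline of ≥ 0.3 logMAR (15 letters, 3 ETDRS lines) in either eye, at each post-baseline visit (Visits 3 to 6) and at the final visit.

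The visit list follows from SAP 9.7.1: "Baseline values will be defined as the last scheduled or unscheduled measurement prior through Visit 2". Visit 3 should stay in but be labelled pre-dose in the table. Acuity is the first ophthalmic procedure listed there, and Protocol 7.1.3 says: "Administer first dose of study drug in clinic after IOP is taken".

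The cost is one SAP sentence; no new data are needed.

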9.7.1.6.3. Slit-Lamp Biomicroscopy

The frequency and percentage of subjects with observed values of each category as well as the categorical shift from baseline at each post-baseline visit will be tabulated at each scheduled visit for both eyes for the following measures of interest: anterior chamber cell, anterior chamber flare,

and conjunctive hyperemia. The percentages are calculated based on the number of subjects at each visit in each treatment group of the Safety Analysis Set.

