9.4.3.3 Other Safety Evaluations

Summary statistics for observed and change from baseline for BCVA, central corneal thickness, and vital signs will be presented. Abnormalities in slit-lamp biomicroscopy and dilated ophthalmoscopy will be summarized by frequency and percentage.

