9.5.1.4.3. Slit-Lamp Biomicroscopy

The slit-lamp biomicroscopy exam will be performed to examine eye structures for each eye at each study visit.

This procedure will be performed in the same manner for all subjects observed at the Investigator's site. The site will record all ABNORMAL findings in the source document and the Investigator will evaluate the ABNORMAL findings as Not Clinically Significant (NCS) or Clinically Significant (CS). CS and NCS ABNORMAL findings will be recorded in the source documentation. However, only ABNORMAL CS descriptions from Visits 3-6 will be captured in the eCRF as AE.

Findings for the anterior chamber (cells and flare), eyelid (hyperemia and edema), conjunctiva (hyperemia, edema (chemosis), discharge/exudate), cornea (edema), iris color, pupil, lashes, and lens will be collected.

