9.5.1.4.4. Central Corneal Thickness

Corneal thickness evaluation (in microns) will be performed using a calibrated ultrasonic or optical pachymeter, provided that the same method is used for all measurements. Measurements will be taken in the central cornea after instilling topical anesthetic. A total of three readings will be obtained for each eye. Care should be taken to place the probe perpendicular to the corneal surface and to not compress the cornea.

Pachymetry is performed at Visit 1 and Visit 6.

- At Visit 1, pachymetry within 3 months of the visit is acceptable.
- At Visit 6, Pachymetry is to be performed after the last IOP measurement.

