9.7.1.6. Analysis of Safety

Safety will be evaluated by AEs, BCVA, slit-lamp biomicroscopy, central corneal thickness, dilated ophthalmoscopy, heart rate and blood pressure, and clinical laboratory tests (blood chemistry, hematology).

The Safety Analysis Set will be used for all safety analyses. All data, including data after rescue, will be summarized as observed and no data imputation will be performed. No statistical treatment group comparisons will be performed, unless otherwise specified. Analyses will be presented by study eye and non-study eye, if applicable.

For by visit summaries, data collected using Early Termination eCRFs will not be summarized unless the termination occurred within the visit windows of a particular visit.

All visits will be included in listings.

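### SAP safety tables are narrower than protocol 9.4.3.3, and this is not declared: 3 of 11 slit-lamp items are tabulated and no corneal thickness change is summarised

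*SAP*

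**What the plan says.** Protocol 9.4.3.3 makes two commitments. For the continuous measures: "Summary statistics for observed and change from baseline for BCVA, central corneal thickness, and vital signs will be presented". For the examinations: "Abnormalities in slit-lamp biomicroscopy and dilated ophthalmoscopy will be summarized by frequency and percentage". Neither sentence restricts the summary to chosen structures.

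SAP 9.5.1.4.3 sets out what the slit-lamp examination records for each eye at each visit: "Findings for the anterior chamber (cells and flare), eyelid (hyperemia and edema), conjunctiva (hyperemia, edema (chemosis), discharge/exudate), cornea (edema), iris color, pupil, lashes, and lens". SAP 9.5.1.4.4 covers corneal thickness, with three readings per eye: "Pachymetry is performed at Visit 1 and Visit 6".

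The safety analysis in SAP 9.7.1.6 opens with "Safety will be evaluated by AEs, BCVA, slit-lamp biomicroscopy, central corneal thickness, dilated ophthalmoscopy", then adds heart rate, blood pressure and laboratory tests. For the slit lamp, 9.7.1.6.3 plans category counts and shifts from baseline "for the following measures of interest: anterior chamber cell, anterior chamber flare", "and conjunctive hyperemia". Subsections 9.7.1.6.1 to 9.7.1.6.6 cover adverse events, visual acuity, slit lamp, dilated ophthalmoscopy, heart rate and blood pressure, and laboratory tests. None covers corneal thickness. The one corneal thickness summary with any detail is at baseline, in 9.7.1.3.1.

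SAP 9.7 says that changes to protocol-specified analyses are described in 9.8. Section 9.8.2 mentions only the handling of rescue and prohibited medication and corrections to the sample code.

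**The concern.** Ocular safety is part of the secondary objective, and this is the first human trial of the compound. Protocol 1.3.1 says that its risks are not yet well understood. In that setting, low-grade findings that differ by dose are what descriptive safety tables should show.

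The slit-lamp list in 9.7.1.6.3 is explicit, so a programmer who follows it will produce three sets of tables and stop. The other items then reach a table only as adverse events. Under protocol Appendix 4 and SAP 9.5.1.4.3, that route is open only to abnormal findings judged clinically significant at Visits 3 to 6. If mild corneal edema or chemosis became more frequent with concentration, and each case was judged not clinically significant, the pattern would sit in subject listings with no count by arm.

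For corneal thickness, the documents state no rule that turns a change into an adverse event. Unless an investigator chose to report one, the Visit 6 values would appear only in listings.

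**Working it through.** No figure stated in the plan bears on this point. The check is a count and a side-by-side reading.

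**Step 1. Slit-lamp items recorded against items tabulated.** Items and scales are from protocol Appendix 4 and agree with the collection list in SAP 9.5.1.4.3. Tables are from SAP 9.7.1.6.3.

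| Item | Scale | Table planned |
|---|---|---|
| Anterior chamber cells | 0–4 | yes |
| Anterior chamber flare | 0–4 | yes |
| Conjunctival hyperemia | 0–3 | yes |
| Chemosis | 0–3 | no |
| Conjunctival discharge | 0–3 | no |
| Corneal edema | 0–3 | no |
| Eyelid hyperemia | 0–3 | no |
| Eyelid edema | 0–3 | no |
| Pupil | normal/abnormal | no |
| Lashes | normal/abnormal | no |
| Lens | normal/abnormal | no |

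- Severity scales: 3 of 8 tabulated, 5 not.
- Normal/abnormal items: 0 of 3 tabulated, 3 not.
- Total: 8 + 3 = 11 items; 3/11 = 27% tabulated; 5 + 3 = 8 without a table.
- Iris colour is left out because it is a description, not a finding, and 9.7.1.3.1 already summarises it at baseline. Counting it gives 3/12 = 25%.

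**Step 2. The five assessments in protocol 9.4.3.3 against the SAP.**

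- Visual acuity: observed and change, SAP 9.7.1.6.2. Met.
- Vital signs: observed and change, SAP 9.7.1.6.5. Met.
- Dilated ophthalmoscopy: categories and shifts, SAP 9.7.1.6.4. Met.
- Slit lamp: 3 of 11 items, SAP 9.7.1.6.3. Met in part.
- Corneal thickness: the protocol asks for observed values and change. The SAP specifies a baseline summary only, with no Visit 6 or change summary.

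Cup-to-disc ratio has the same Visit 1 and Visit 6 schedule, and SAP 9.7.1.6.4 gives it both observed and change summaries. The corneal thickness gap therefore looks like an oversight. The schedule footnote that requires the same pachymetry method at Visits 1 and 6 also suggests that a comparison was intended.

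**Step 3. Declaration.** By the SAP's own rule in 9.7, both reductions belong in 9.8. Neither is in 9.8.2.

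**Step 4. What is still reported.** Clinically significant slit-lamp findings at Visits 3 to 6, in any structure, become adverse events. SAP 9.7.1.6.1 tabulates these by system organ class and preferred term, severity and relationship, with ocular events split by eye. SAP 9.7.1 lists all collected data by subject. The remainder, with no planned summary by arm, is (a) findings judged not clinically significant on the 8 untabulated items and (b) corneal thickness at Visit 6 and its change.

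**The case against.** The best defence is that the SAP still covers the ground in general terms. Its synopsis bases the safety assessment on a list that includes corneal thickness, summarised by treatment group and by eye. Section 9.7.1.6 says that all data will be summarised as observed, and the protocol's own commitment remains in force. Clinically significant findings are tabulated as adverse events, and visual acuity has its own analysis. The tables at issue are descriptive, involve about 60 subjects, and carry no planned treatment comparison.

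Much of this stands. A reader might infer that corneal and lid safety goes unsummarised. The documents do not support that, because clinically significant corneal and lid findings reach the adverse event tables. A reader might also infer that the SAP contradicts the protocol on corneal thickness. It does not: no SAP text excludes the change summary, and the measure is named as a safety variable. It is an omission under a general commitment. The protocol, moreover, asks only for the frequency and percentage of abnormalities, so grade and shift tables for every item would exceed it.

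The defence does not close the gap. The sentence about summarising data as observed deals with post-rescue data and imputation. It specifies no change statistic and does not override the explicit slit-lamp list. The protocol promised a summary of abnormalities, not only of clinically significant ones. A listing is neither a frequency table nor a comparison of arms.

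**Conclusion.** The point holds as a gap between protocol and SAP that should be closed. The SAP tabulates 3 of 11 slit-lamp items, specifies no Visit 6 or change summary for corneal thickness, and declares neither. The loss is limited to the two remainders in step 4 of the working. No success rule, error rate or sample size depends on it.

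A reader might go further and infer that an unexamined change in corneal thickness weakens the primary endpoint, because IOP is measured by applanation. The documents do not carry that argument. They tie corneal thickness to IOP interpretation only at entry, and they give no figure for IOP error per micron and no expected change over three weeks. Pachymetry after baseline is done only at Visit 6, so it cannot speak directly to Days 7 and 14, which supply 2 × 3 = 6 of the 9 primary time points.

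The conclusion assumes that all slit-lamp items are entered in the database, as the collection statement in SAP 9.5.1.4.3 indicates, and that the list in 9.7.1.6.3 is meant to be complete.

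**What to change.** Two additions to the SAP:

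- **Corneal thickness.** Add a subsection to 9.7.1.6. Use the mean of the three readings, and summarise observed values at Visits 1 and 6 and the change between them, by arm, separately for study and non-study eye.
- **Slit lamp.** Extend 9.7.1.6.3 so that the other 8 items have the frequency and percentage of abnormalities at each visit, by arm and eye. State what counts as abnormal on the 0–3 scales (for example, any grade above 0). Shift tables for these items are optional.

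If the sponsor prefers the shorter slit-lamp list, 9.8.2 should declare the reduction and give the reason.

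The cost is a few more descriptive tables. The data are already due to be collected, and neither the efficacy analysis nor the sample size changes.
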